- Consumption of large quantities of methylxanthine-containing beverages (more than 600 mg caffeine/day: 1 cup (250 mL) of coffee contains approximately 100 mg of caffeine, 1 cup of black or green tea contains approximately 30 mg and 1 glass of cola contains approximately 20 mg caffeine)
- Volunteers who took an investigational product (in another clinical trial) by prescription within 2 weeks or an over-the-counter medication taken within 1 week before drug administration.

Investigational Medicinal Product: dose/mode of administration/ dosing schedule:

5 mg/5 mg bisoprolol-amlodipine combination tablet (Concor AM®) administered either as a single dose on Day 1 or a single dose on Day 15 of the trial.

Reference therapy: dose/mode of administration/dosing schedule:

5 mg bisoprolol tablet (Concor®) and 5 mg amlodipine tablet (Norvasc®) administered concomitantly either as a single dose on Day 1 or a single dose on Day 15 of the trial.

Planned trial and treatment duration per subject:

The planned treatment consists of initial screening assessments (within 7 days prior to the first trial drug administration) followed by 2 trial periods consisting of 8 days of blood sampling in a crossover trial design. Each trial period includes a single dose of trial drug administration and the doses are separated by a 14-day Washout period. An End of Trial visit (Day 29) will be conducted 14 days after administration in Period 2. The overall trial duration for each subject is approximately 5 weeks (or approximately 35 days) including the Screening and End of Trial visit.

Statistical methods:

Based on the results of the previously conducted BE trial, a within-subject coefficient of variation (CV) for AUC_{0-t} and C_{max} has been calculated. The sample size in fasting cohort calculation is mainly driven by AUC_{0-t} of amlodipine due to the largest ratio (111.22%) of geometric least square mean and intra-subject CV (10.4%). With 12 evaluable subjects at least 80% power can be achieved for all 4 parameter's 90% confidence intervals of the treatment ratio to fall within 80.00% to 125.00%. Taking account of the possible dropout, 4 additional subjects will be enrolled. In the case of full completion by all 16 subjects, a power of > 90% may be achieved. Assume there is no difference between fasting and fed states [10, 11], a total of 32 subjects are planned to be enrolled.

Bioequivalence Trial of Concor AM[®] vs Bisoprolol and Amlodipine in Chinese Subjects

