Note: Statistically powered for both fasting and fed cohorts.

The Fasting and Fed Cohorts can be scheduled in parallel or "staggered" to finish one cohort completely before the other cohort starts.

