5.5 Criteria for Subject Withdrawal

5.5.1 Withdrawal from Trial Therapy

Subjects are free to discontinue the trial at any time without giving their reasons. A subject must be withdrawn in the event of withdrawal of the subject's consent.

Subjects who withdraw from the trial will also be withdrawn from the investigational medicinal product (IMP). Dropout will not be replaced for this trial as long as the minimum evaluable sample size is met.

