5.5.2 Withdrawal from the Trial

Furthermore, participation in this clinical trial can be discontinued by the Investigator for one of the following reasons:

- 1. On Day 1 before trial drug administration of Period 1 and additionally on Day 15 before trial drug administration of Period 2, if the supine blood pressure before drug administration is below 100/65 mmHg or above 139/90 mmHg, the subject has to be withdrawn from the trial
- 2. Adverse events, as assessed by the Investigator to affect the outcome of the trial endpoints
- 3. Significant protocol violation such as restrictions regarding alcohol and drug use, and nonadherence to the fasting or fed state
- 4. Difficulties with blood collection
- 5. Emesis experienced within 16 hours following drug administration because of incomplete absorption (this period of time corresponds also to 2 times the median time of maximum plasma concentration observed [t_{max}] of amlodipine). Subjects experiencing vomiting later than 16 hours postdose will not be withdrawn unless otherwise decided by the Investigator in light of subject's safety or trial integrity
- 6. Subject is uncooperative during the trial
- 7. Use of any medication
- 8. Withdrawal by Investigator's judgement.

Concomitant medication of any drug is prohibited. Any possible drug interaction caused by a concomitant medication with the IMP during the trial must be completely avoided in this trial.

Details of reasons for premature withdrawal of subjects will be recorded and documented in the final report.

In case of premature withdrawal from the trial, the investigations scheduled for premature withdrawal visit should be performed, if possible, with focus on the most relevant assessments (Section 7.1, "Schedule of Assessments" and Table 1). In any case, the appropriate electronic Case Report Form (eCRF) section must be completed.

Dropouts within each sequence will be replaced if the total number of evaluable subjects within the sequence falls below 12 (Section 8.2.1).

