8.2 Statistical Analysis

8.2.1 Sample Size

The BE is declared if all comparisons in primary hypothesis achieve the criteria – the 90% CIs for the ratios between the investigational product and comparators of geometric means of both AUC_{0-t} and C_{max} for bisoprolol and amlodipine in plasma are within 80.00% to 125.00%.

Based on the results of a BE trial conducted in 2008 by PPD where a higher dose strength 10 mg/10 mg fixed-dose-combination tablet was tested against respective single agent of bisoprolol and amlodipine, the expected effects in fasting state is presented below.

subjects at least 80% power can be achieved for all 4 parameter's 90% CIs of the treatment ratio to fall within 80.00% to 125.00%. Taking account of the possible dropout, 4 additional subjects will be enrolled. In the case of full completion by all 16 subjects, a power of > 90% may be achieved.

Sample Size and Power Calculation Results

Sample Size	Power (%) for Bisoprolol		Bisoprolol Power (%) for Amlodipine		Joint Power (%)
	C_{max}	AUC_{0-t}	C _{max}	AUC _{0-t}	
10	100.00	99.59	96.27	74.30	71.24
12	100.00	99.92	98.56	82.13	80.88
14	100.00	99.98	99.46	87.71	87.22
16	100.00	100.00	99.80	91.63	91.45

 $AUC_{0:t}$ = area under the (plasma) concentration-time curve from time 0 to time t; C_{max} = the maximum plasma concentration observed

Historical data showed no food effect on PK for either drugs, bisoprolol and amlodipine respectively [10, 11], and the observed variability has been comparable between fasting and fed dosing states. By applying statistical powering also to the fed cohort, assuming the intra-subject variability is similar in fed state with standard meal consumption [10, 11]. Based on the sample size calculation above, a 16-subject trial (12 subjects with adequate power and 4 subjects to cover potential dropout) provides at least 80% power to meet the BE criteria for both parameters and both products.

Sensitivity analysis has been performed to explore impact of potentially different variability on the sample size and power calculation. The outcome, as selectively displayed in the tables below, suggests that consistently high power (80%+) can be obtained with the proposed sample size.

Sensitivity Analysis 1:

Assume 5% variation for all ratios (95% \sim 105%) and 10% all intra-subject CV.

Comple Size	Power (%) for Bisoprolol		Power (%) for Amlodipine		Isint Dames (0/)
Sample Size	C _{max}	AUC _{0-t}	C _{max}	AUC _{0-t}	Joint Power (%)

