10	96.83	96.83	96.83	96.83	87.89
12	98.83	98.83	98.83	98.83	95.42
14	99.58	99.58	99.58	99.58	98.34
16	99.85	99.85	99.85	99.85	99.42

 AUC_{0-t} = area under the (plasma) concentration-time curve from time 0 to time t; CV = coefficient of variation; C_{max} = the maximum plasma concentration observed

Sensitivity Analysis 2:

Assume 5% variation for all ratios (95% \sim 105%) except of Amlodipine AUC_{0-t} (90% \sim 110%), and 10% all intra-subject CVs.

Sample Size	Somple Size Power (%) for Bisoprolol		Power (%) for Amlodipine		Laint Dawan (9/)
Sample Size	Cmax	AUC _{0-t}	Cmax	AUC _{0-t}	Joint Power (%)
10	96.83	96.83	96.83	77.74	70.56
12	98.83	98.83	98.83	85.17	82.23
14	99.58	99.58	99.58	90.25	89.13
16	99.85	99.85	99.85	93.66	93.26

 AUC_{0-t} = area under the (plasma) concentration-time curve from time 0 to time t; C_{max} = the maximum plasma concentration observed

Randomization

Each eligible subject will be allocated to a treatment sequence according to a computer-generated randomization schedule. Subjects will be identified only by their assigned subject number. The subjects will receive consecutive subject numbers in the order of their enrollment into the trial.

A total of 32 eligible healthy male and female Chinese subjects (16 in fasting cohort and 16 in fed cohort) who meet the eligibility criteria will be randomized (with each gender representing no less than 1/3 of the total number) on Day 1 in a 1:1 ratio to one of 2 treatment sequences: Sequence A-B or Sequence B-A as presented in Table 5.

In sequence A-B, subjects will receive bisoprolol-amlodipine 5 mg/5 mg combination tablets (Treatment A) in Period 1 and bisoprolol 5 mg tablets and amlodipine 5 mg tablets given concomitantly (Treatment B) in Period 2. In sequence B-A, subjects will receive bisoprolol 5 mg tablets and amlodipine 5 mg tablets given concomitantly (Treatment B) in Period 1 and bisoprolol-amlodipine 5 mg/5 mg combination tablets (Treatment A) in Period 2.

Table 5 Randomization Allocation

	Day 1 of Period 1	Day 1 of Period 2
Fasting cohort (n= 16)	Treatment A (n= 8)	Treatment B (n= 8)
rasting conort (n= 10)	Treatment B (n=8)	Treatment A (n= 8)
End only out (n = 16)	Treatment A (n= 8)	Treatment B (n= 8)
Fed cohort (n= 16)	Treatment B (n=8)	Treatment A (n= 8)

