The first 4 discontinued subjects of each cohort not be replaced. Subjects will only be replaced if the number of subjects within a sequence falls below 12. The subject who is replacing a discontinued subject will then be allocated to the treatment sequence of the subject who discontinued.

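### The replacement floor of 12 is set per sequence, but each cohort has only 8 per sequence; 12 is the cohort total behind the 80% power claim

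*Protocol*

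**What the plan says.** The power basis is a cohort total. The synopsis (Statistical methods) says "With 12 evaluable subjects at least 80% power can be achieved", and Protocol section 8.2.1 explains each cohort of 16 as "12 subjects with adequate power and 4 subjects to cover potential dropout". Table 5 splits each cohort 8 and 8 between the two sequences. SAP section 6 confirms that sequences are assigned within each food group.

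The replacement rule appears in several forms:

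- Protocol 5.5.1: "Dropout will not be replaced for this trial as long as the minimum evaluable sample size is met".
- Protocol 5.5.2: "Dropouts within each sequence will be replaced if the total number of evaluable subjects within the sequence falls below 12".
- Protocol 8.2.1, two consecutive sentences: "The first 4 discontinued subjects of each cohort not be replaced", then "Subjects will only be replaced if the number of subjects within a sequence falls below 12".
- Protocol 8.2.4.4 starts replacement in a sequence once it has lost 4 subjects and has 12 left.
- SAP section 7 repeats both sentences of Protocol 8.2.1, with group in place of cohort.

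The note to Figure 2 in Protocol 5.1 allows the cohorts to run in parallel or to be staggered "to finish one cohort completely before the other cohort starts".

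**The concern.** A site must be able to apply a replacement threshold, and this one does not work on either literal reading of sequence.

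**Within a cohort.** A sequence starts at 8, already under 12. Every dropout would then call for replacement, against the sentence that exempts the first 4 of each cohort. This errs towards replacing too many and costs no power.

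**Pooled over cohorts.** A sequence starts at 8 + 8 = 16, so 12 is at least possible. But with staggered cohorts a sequence holds at most 8 while the first cohort runs, so the floor cannot be used. With parallel cohorts it protects the wrong quantity. SAP section 16.1 fits the model separately by food condition and requires all 4 endpoints to pass in both groups, so a shortfall in one cohort lowers power for the primary objective.

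The counted unit also drifts: evaluable subjects in 5.5.2, subjects in 8.2.1 and SAP 7, subjects remaining in 8.2.4.4.

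**Working it through.** **Inputs.** For amlodipine AUC0-t, which drives the sample size, the ratio is 1.1122 and the intra-subject CV 10.4% (synopsis). The limits are 80.00% to 125.00% with a 90% CI, i.e. two one-sided tests at 0.05 (Protocol 8.2.4.2). The design is a 2×2 crossover with n1 and n2 subjects per sequence.

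**Formula.** σw = √ln(1 + 0.104²) = 0.1037. SE = σw·√[0.5(1/n1 + 1/n2)], df = n1 + n2 − 2. Power is the exact probability that both one-sided tests reject, integrated over the distribution of the residual variance.

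**Step 1: reproduce the plan.**

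| n1/n2 | Cohort total | Power | Plan (amlodipine AUC0-t) |
|---|---|---|---|
| 5/5 | 10 | 74.30% | 74.30% |
| 6/6 | 12 | 82.13% | 82.13% |
| 7/7 | 14 | 87.71% | 87.71% |
| 8/8 | 16 | 91.63% | 91.63% |

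The plan's joint power is the product of its four columns. At 12 this is 1.0000 × 0.9992 × 0.9856 × 0.8213 = 80.88%, as stated. So 12 is the total over both sequences of one cohort. Twelve in each sequence would mean 24 per cohort (98.35%), more than the 16 enrolled.

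**Step 2: the within-cohort reading.** 8 < 12 at zero dropouts, whereas the exemption of the first 4 gives 16 − 4 = 12 per cohort. The two sentences conflict.

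**Step 3: the pooled reading, by example.** One cohort loses 3 from one sequence and 2 from the other; the other cohort loses none. The pooled sequences stand at 16 − 3 = 13 and 16 − 2 = 14, so the sequence rule forbids replacement. The affected cohort has 5 + 6 = 11. Section 5.5.1 no longer waives replacement at 11, and the fifth dropout is outside the exempt 4. The protocol points both ways.

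**Step 4: power at 11.** With 6/5, SE = 0.1037 × √[0.5(1/6 + 1/5)] = 0.0444 and df = 9. Power for amlodipine AUC0-t is 78.24%. For joint power, take the plan's other three columns at 10 and at 12 as bounds:

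- lower: 0.7824 × 1.0000 × 0.9959 × 0.9627 = 75.0%
- upper: 0.7824 × 1.0000 × 0.9992 × 0.9856 = 77.1%

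The extreme the pooled floor permits is 4 lost from each sequence, all in one cohort. That leaves 4/4 and 63.51% for amlodipine AUC0-t.

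**Step 5: how often.** The documents give no dropout rate, so the rates below are assumptions. Further assumptions are independent dropout, cohorts in parallel with dropouts in random order, the first 4 per pooled sequence unreplaced, and later ones replaced in the same cohort by subjects who complete.

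| Assumed dropout | P(at least one cohort below 12) | Of these, smaller cohort has exactly 11 |
|---|---|---|
| 5% | 0.15% | 92.2% |
| 10% | 2.7% | 85.5% |
| 15% | 10.8% | 80.0% |
| 25% | 38.4% | 72.3% |

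The 25% row equals the plan's whole allowance (4 of 16) and is not an expected rate.

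**The case against.** The strongest reply is that the intent is plain. The sentence on the first 4 dropouts of each cohort, with 16 per cohort, already implies a cohort floor of 12. Section 5.5.1 ties replacement to a minimum evaluable size that the power section puts at 12 of 16. The arithmetic in 8.2.4.4 (4 lost, 12 left) fits a cohort of 16 as well as it fits a pooled sequence. Assignment to sequence within each food group and the option to stagger both speak against pooling. All of this stands, and it limits the practical effect. What remains is that four places name the wrong unit, and the restrictive wording in 8.2.1 and SAP 7 can block a replacement that 5.5.1 leaves open.

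A reader might infer more, which the documents do not support:

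- *That the trial is underpowered or the calculation wrong.* The power figures reproduce to two decimals.
- *That exclusions from the PK Analysis Set should also trigger replacement.* SAP 10.2 excludes for a predose concentration above 5% of Cmax, which is known only after bioanalysis. In an open-label trial, added enrolment would then depend on concentration data.
- *That a minimum per sequence is needed.* Twelve split 8/4 gives 78.06% for amlodipine AUC0-t, but the plan nowhere promises 80% for every split. That is a separate design preference.

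**Conclusion.** The inconsistency is real: a stated decision threshold cannot be followed as written in Protocol 5.5.2, 8.2.1 and 8.2.4.4 and SAP 7. A cohort floor of 12 was very probably meant, and under it nothing is lost. Power falls only if someone applies the pooled reading. The usual loss is then from 12 to 11 in one cohort, about 4 points for amlodipine AUC0-t (82.13 − 78.24 = 3.89) and about 4 to 6 points of joint power (80.88 − 77.1 = 3.8; 80.88 − 75.0 = 5.9). At assumed dropout of 5% to 10%, that would happen in fewer than 3% of trials. These sizes rest on the plan's own ratio and CV and on the assumptions in step 5. Type I error, the model and the acceptance limits are unaffected. It is worth correcting because the correction is cheap, not because the trial is at serious risk.

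**What to change.** In all four places, replace the sequence-level floor with one cohort-level rule. Possible wording: *In each cohort (fasting or fed), up to 4 discontinued subjects are left unreplaced; any further discontinued subject is replaced, so that at least 12 subjects per cohort complete both periods. The replacement joins the same cohort and sequence as the subject replaced.*

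Count discontinuations or completion of both periods, both known without concentration data, and use that one term throughout. Point the minimum in 5.5.1 to the same number. Do not tie the trigger to PK Analysis Set exclusions determined after bioanalysis.

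The cost is wording in four places plus the cross-reference. In a given trial there may be a few replacements that the pooled reading would not trigger. The expected number is the same under either floor, since both allow 4 losses of 16: 2·E[max(0, Bin(16, p) − 4)] = 0.002, 0.04, 0.22 or 1.35 per trial at assumed dropout p of 5%, 10%, 15% or 25%.

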8.2.2 Endpoints

8.2.2.1 Primary Endpoints

The primary endpoints are the following PK parameters calculated from bisoprolol and amlodipine plasma concentrations:

- AUC_{0-t} of bisoprolol
- C_{max} of bisoprolol
- AUC_{0-t} of amlodipine
- C_{max} of amlodipine

8.2.2.2 Secondary Endpoints

The secondary endpoints are the following PK parameters determined from plasma concentrations of both analytes, bisoprolol and amlodipine:

- t_{max}
- t_{1/2}
- AUC_{0-∞}
- AUC_{extra}
- λ_z
- CL/f
- \bullet V_{ss}/f

All PK parameters (primary endpoints and secondary endpoints) will be calculated from plasma concentrations of bisoprolol and amlodipine by applying non-compartmental analysis methods according to respective SOPs.

8.2.2.3 Safety Endpoints

Safety and tolerability will be assessed by monitoring of:

- Assessment of general safety and tolerability
- Adverse Events
- Vital signs (blood pressure, pulse rate, temperature and respiration)
- Biochemistry, hematology, and urinalysis
- Computerized 12-lead ECG recordings (including QTc evaluation)
- Physical examination

8.2.3 Analysis Sets

Per-protocol population

The per-protocol population includes all randomized subjects who have been treated according to protocol and fulfill the following criteria:

- All inclusion/exclusion criteria satisfied, unless some criteria were waived by the Investigator/Sponsor
- Absence of relevant protocol violations with respect to factors likely to affect the comparability of PK results
- Adequate investigational product compliance
- Primary PK variables AUC_{0-t} and C_{max} of bisoprolol or amlodipine in plasma should be available for both trial treatments

If subjects received concomitant medication for the treatment of AEs within 48 hours after dosing, their inclusion in the per-protocol population should be approved by the Sponsor.

Safety population

The safety population includes all subjects who received at least 1 dose of trial drug. In general, clinical data will be analyzed for the safety population.

Pharmacokinetic population

The PK Population may include all subjects who completed the trial with adequate trial medication compliance, without any relevant protocol violations with respect to factors likely to affect the comparability of PK results, and with sufficient evaluable data to determine primary endpoints (AUC_{0-t} and C_{max}) for both treatments in both cohorts. If subjects would receive concomitant medication for the treatment of an AE, their inclusion in the PK Population will be decided on a case-by-case basis. All PK analyses will be based on this population analysis set.

8.2.4 Description of Statistical Analyses

8.2.4.1 General Considerations

Details of the statistical analysis will be presented in a statistical analysis plan prior to database lock.

The statistical analysis will not be started until all data have been corrected and checked for plausibility, and until all necessary coding and assessments have been completed.

All data recorded during the trial will be presented in individual data listings performed on the safety population. All data will be evaluated as observed values; no imputation method for missing values will be used. Methods for concentration data below the lower limit of quantification will be described in the statistical analysis plan. The consideration of covariates in the mixed effect model is not planned.

All statistical analyses will be performed by Merck (Darmstadt, Germany).

8.2.4.2 Analysis of Primary Endpoints

The null and alternative hypotheses are the following, to be applied to both treatments:

$$H_0: for\ AUC_{0-t}\ \mu_T\ /\ \mu_C \le 0.8\ or\ \mu_T\ /\ \mu_C \ge 1.25$$
 for at least 1 primary endpoint $for\ C_{\max}\ \mu_T\ /\ \mu_C \le 0.8\ or\ \mu_T\ /\ \mu_C \ge 1.25$

$$H_1$$
: for AUC_{0-t} 0.8 < μ_T/μ_C < 1.25 for C_{\max} 0.8 < μ_T/μ_C < 1.25 , for all 4 primary endpoints

where μ_T and μ_C are the means of primary endpoints following investigational product and comparators (Treatment A and Treatment B), respectively.

The analysis of primary endpoints will be based on PK Population (Section 8.2.3)

The primary variable, C_{max} and AUC_{0-t} in fasting or fed cohort will be log-transformed and mixed effect model will be applied. The model will include effects for sequence, treatment and period. Subject within sequence will be included as random effect.

Based on the residual (within-subject) variation, 90% CIs for the ratio of geometric means will be calculated. The BE can be established if all the 4 sets of the 90% CIs on the ratios between investigational product and comparators of the geometric means fall within 80.00% to 125.00%.

8.2.4.3 Analysis of Secondary Endpoints

For t_{max} , the Hodges-Lehmann estimates [9] for the pairwise treatment differences and the corresponding 90% CIs according to the Tukey method will be calculated.

The mixed model as described above will also be applied to AUC_{0-∞}. A 90% CI will be calculated for the ratios of geometric means of the investigational product and comparators (eg, Treatment A/Treatment B).

Summaries using descriptive analyses for the remaining PK parameters and the safety variables will be performed as described in Section 8.2.4.4 and Section 8.2.4.5.

8.2.4.4 Analysis of Safety Endpoints

All data recorded during the trial will be presented in individual data listings performed on the safety population.

All safety variables will be analyzed using descriptive statistics.

For the evaluation of safety parameters, the continuous variables will be summarized descriptively per treatment, period, time point, and overall by N, arithmetic mean, median, standard deviation (SD), standard error of the mean (SEM), and minimum and maximum values. Categorical variables will be presented in frequency tables with the counts of observations and corresponding percentages.

Blood pressures, pulse rate measurements and ECG recordings will be individually listed by treatment, subject number, period, and time point, and the abnormal values flagged according to reference laboratory ranges. All hematology and biochemistry parameters will be listed and summarized using descriptive statistics by treatment, period, and time point on observed values. Urinalysis will be summarized in frequency tables.

After coding of AEs according to the Medical Dictionary for Regulatory Activity classification (current version) and assignment to a system organ class and preferred term, all AEs recorded during the course of the trial will be listed by treatment and subject number.

The AE listings will include the following items:

- System organ class
- Preferred term
- Investigator's description
- Whether the event is treatment-emergent
- Trial treatment at onset of event
- Date and time of onset and resolution
- Duration of the event
- Date and time of last administration before AE
- Intensity
- Causality relationship to investigational product
- Outcome

- Action taken to investigational product
- Other action
- Seriousness

Incidence of treatment-emergent adverse events will be summarized using frequency of events and number of subjects experiencing these events per treatment, preferred term, and system/organ class.

In addition, all treatment-emergent adverse events will be tabulated by intensity and relationship to drug per treatment and cohort. An AE will be considered "treatment-emergent" if it occurred after the first investigational product administration or if it occurred before the first investigational product administration and worsened after.

Results of physical examination will only be listed by treatment, subject, period, time point, and body system.

Handling of discontinued subjects and missing data

If 4 subjects within one sequence have already discontinued and 12 subjects remain in that sequence, any further discontinued subjects will be replaced in this sequence.

